11.3.4 Suspected Unexpected Serious Adverse Reactions

The sponsor has a legal responsibility to notify, as appropriate and according to local regulations, both the local regulatory authority and other regulatory agencies about the safety of the product under clinical investigation. Prompt notification of SAEs by the investigator to the sponsor is essential so that legal obligations and ethical responsibilities towards the safety of patients are met.

The sponsor will ensure that all relevant information about Suspected Unexpected Serious Adverse Reactions (SUSARs) is recorded and reported as soon as possible, but within a maximum of 15 days (fatal or life-threatening SUSARs within a maximum of seven days) of first knowledge by the sponsor or designee, to the competent regulatory authorities and/or to the Ethics Committee according to the applicable local regulatory requirements. Relevant follow-up information of fatal or life-threatening SUSARs will be communicated subsequently within an additional eight days.

The investigator should be aware of local reporting regulations to the IEC/IRB. The Safety CRO will either supply the investigator with the reports which should be passed on to the IEC/IRB or report directly to the IEC/IRB depending on local regulations.

11.4 Reporting of Adverse Events after Termination of Trial Participation

Any suspected IMP-related SAE, non-serious grade ≥ 2 ocular AEs and non-serious grade ≥ 3 AEs occurring at any time after the patient has terminated trial participation, should be emailed to the Safety CRO at [REDACTED] if there is access to a secured email, or if there is no access to a secured email, faxed to [REDACTED].

11.5 Timelines for Reporting

The required timeframes and reporting forms for reporting SAEs, non-serious grade ≥ 3 AEs, non-serious grade ≥ 2 ocular AEs, overdose and/or medication errors and pregnancies are presented in [Table 3](#).

All new information regarding SAEs, non-serious grade ≥ 3 AEs, non-serious grade ≥ 2 ocular AEs, overdose and/or medication errors and pregnancies (initial and follow-up) must be reported from sites to the Safety CRO within 24 hours. Sites must respond to follow-up queries from the Safety CRO within 3 days.

Please note that any SAE should be reported on an SAE Report Form, any non-serious grade ≥ 3 AE should be reported on a Non-serious Grade 3 Adverse Event Report Form, any non-serious grade ≥ 2 ocular AE should be reported on a Non-serious Grade 2 Ocular Adverse Event Report Form, and any pregnancy should be reported on a Pregnancy Form. Overdose and medication errors have no specific reporting form and should be reported on the SAE Report Form regardless of seriousness. If the event is serious, the serious criteria tick box should be ticked, and if the event is non-serious, the serious criteria tick box shall be left blank.

Table 3: Timeframes for Reporting SAEs, Non-serious Grade ≥ 3 AEs, Non-serious Grade ≥ 2 Ocular AEs, Overdose and/or Medication Errors and Pregnancies

Type of Event	Initial Reports		Follow-up Information on a Previous Report	
	Time Frame	Documents	Time Frame	Documents
SAE	24 hours*	SAE Report Form	3 days* 24 hours*	CDS SAE DCF Site SAE DCF
Non-serious grade ≥ 3 AE	24 hours*	Non-serious Grade 3 Adverse Event Report Form	3 days* 24 hours*	CDS SAE DCF Site SAE DCF
Grade ≥ 2 ocular AE	24 hours*	Non-serious Grade 2 Ocular Adverse Event Report Form	3 days* 24 hours*	CDS SAE DCF Site SAE DCF
Overdose and/or Medication Errors	24 hours*	SAE Report Form	3 days* 24 hours*	CDS SAE DCF Site SAE DCF
Pregnancy	24 hours*	Pregnancy Form	3 days	Updated Pregnancy Form

AE=adverse event; CDS=Corporate Drug Safety; DCF=Data Clarification Form; SAE=serious adverse event

** No later than 24 hours following a) the patient visit at which such AE was reported, noted or recognized; or b) the principal investigator's or any investigator personnel's receipt of the test results or other information at, or from which, such development was reported, noted or recognized.*

11.6 Recording Instructions

11.6.1 Start Date and Time

Start date for (S)AEs is the date of occurrence of the first symptom of the disease, e.g., if chest pain occurs on 01 April 2016 and the patient is hospitalized with myocardial infarction on 04 April 2016, the onset date of the SAE myocardial infarction is 01 April 2016.

Time should be filled in if event starts on a dosing day or if the duration of the event is less than 24 hours.

11.6.2 End Date and Time

End date should be filled in if the outcome of an event is fatal, recovered/resolved, or recovered/resolved with sequelae.

Time should be filled in if the duration of the event is less than 24 hours.

11.6.3 Diagnosis

The diagnosis of an AE should be recorded if available. If no diagnosis is available each sign and symptom should be recorded as individual AEs.

Study Disease:

Signs and symptoms, which according to the investigator are expected and well-known consequences of the indication, both in intensity and frequency, should not be reported as AEs or SAEs. Any unexpected change in the intensity or frequency should be reported as an AE (or SAE, if applicable).

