7. TRIAL OBJECTIVES AND ENDPOINTS

Objectives	Endpoints
Primary 
The primary objective of the trial is to collect long-term safety data from patients with solid tumors who have been treated with tisotumab vedotin and completed any base trial (i.e., GEN701 or GEN702)	
Adverse events
Secondary 
To further evaluate the anti-tumor activity of tisotumab vedotin	
Objective response rate assessed by tumor shrinkage (according to the Response Evaluation Criteria In Solid Tumors version 1.1 [RECIST 1.1]) including change in prostate specific antigen (PSA) for patients with prostate cancer and CA 125 for patients with ovarian cancer

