11. ASSESSMENT AND REPORTING OF ADVERSE EVENTS

11.1 Definitions

11.1.1 Adverse Event

An AE is any untoward medical occurrence in a patient or clinical trial patient, temporally associated with the use of a medicinal product, whether or not considered related to the medicinal product.

NOTE: An AE can therefore be any unfavorable and unintended sign (including an abnormal laboratory finding), symptom, or disease (new or exacerbated) temporally associated with the use of a medicinal product.

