11.1.3 Adverse Events of Special Interest

Based on the currently available safety profile for tisotumab vedotin, the below listed events are regarded as adverse events of special interest (AESIs):

- Bleeding-related events
- Neuropathy
- Ocular events (conjunctivitis, ulceration, keratitis, symblepharon)

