11.2 Adverse Event Reporting

The investigator must report all directly observed AEs and all AEs reported by the patient. A general type of question should be used similar to “Do you have any health problems?” or “Have you had any health problems since your last visit?”

All AEs must be reported from the time the patient signs the ICF until 30 days after the last dose of tisotumab vedotin, or until the patient withdraws consent or starts subsequent anti-cancer therapy, whichever occurs first.

Any AE (signs, symptoms and diagnosis) occurring prior to signing the ICF must be recorded in the applicable base protocol eCRF.

Registration of Adverse Events in the eCRF:

- All AEs must be recorded in the eCRF.
- Grade 3 and 4 abnormal laboratory test results must be reported as AEs when these are assessed as clinically significant by the reporting investigator.

Reporting of Adverse Events to the Safety CRO:

- All SAEs
- Ocular grade ≥ 2 AEs
- All non-serious grade ≥ 3 AEs
- All events of overdose and/or medication errors, independent of intensity, must be reported as AEs to the Safety CRO.
- Any event of pregnancy must be reported as an AE to the Safety CRO.

Please refer to Section 11.5 for an overview of AE reporting timelines.

All deaths (including deaths due to disease progression) should be reported as an SAE.

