5.3 Inclusion and Exclusion Criteria

Listing of all inclusion and exclusion criteria not met together with the protocol version will be provided.

6. Demographic and Baseline Disease Characteristics

In the listing of demographic characteristics, the variables to be listed are:

- Gender (Male/Female)
- Age (Years), date of birth
- Race (White, Black or African American, Native Hawaiian or other Pacific Islander, Asian, American Indian or Alaska native, Other + details)
- Ethnicity (Hispanic or Latino, Not Hispanic or Latino)
- ECOG performance score (0-5). Note: at entry only patients with an ECOG performance score of 0 and 1 are allowed.

 Confidential

- Childbearing potential (Yes/No and reason)
- Cancer type (Ovary, Cervix, Endometrium, Bladder, Prostate, Head and neck, Esophagus, Lung)

7. Medical History

Medical conditions will be coded using the Medical Dictionary for Regulatory Activities (MedDRA).

The medical conditions will be listed including term, system organ class and preferred term, start and end date, ongoing flag and started more than 1 year ago flag.

The medical history from the base trial will be reported.

8. Subsequent Cancer Therapies

All subsequent cancer therapies, except for surgeries, will be listed including the anatomical therapeutic chemical (ATC) code level 2 and active ingredient (WHO-DD dictionary). Surgeries will be coded using the Medical Dictionary for Regulatory Activities (MedDRA) and presented including system organ class and preferred term.

9. Prior and Concomitant Medications

Prior and Concomitant medications will be classified according to World Health Organization Drug Dictionary.

Medications will be flagged according to the following 3 distinct categories:

[figure not shown]
- Prior when they start and end before the first day of trial treatment.
- Prior and ongoing when they start before the first day of trial treatment and stop or continue after the first day of trial treatment.
- Medications will be reported as concomitant when they start on or after first day of trial treatment.

A listing of all medications recorded on the (prior and) concomitant medications CRF page will provide details including indication, dose, route, frequency, start and stop dates, prior/concomitant flag, active ingredient and ATC class.

10. Efficacy Evaluation

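### Protocol 11.6.3 exempts signs judged expected for the tumor from AE reporting with no carve-out for AESIs, so some non-fatal tumor-site bleeding may be missing from the primary endpoint

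*Protocol*

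**What the plan says.** The sole primary endpoint in Protocol Section 7 is "Adverse events". Section 11.1.1 defines an AE as any untoward occurrence "whether or not considered related to the medicinal product". Section 11.2 states: "The investigator must report all directly observed AEs and all AEs reported by the patient". It also requires every AE to be entered in the eCRF.

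The study-disease paragraph of Section 11.6.3 sets a different rule. It opens "Signs and symptoms, which according to the investigator are expected" and goes on to say that such "expected and well-known consequences of the indication, both in intensity and frequency, should not be reported as AEs or SAEs". The next sentence limits this: "Any unexpected change in the intensity or frequency should be reported as an AE (or SAE, if applicable".

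Section 11.1.3 lists three AESIs. The first is "Bleeding-related events", with no restriction on cause, site or grade. Neither 11.1.3 nor 11.6.3 says how the two provisions interact. SAP 11.2 handles AESIs by adding a flag to adverse events that are already in the listing.

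**The concern.** Section 11.6.3 makes an event's entry into the database depend on the investigator's view of what the tumor would be expected to produce, with no list or criteria. For most symptoms this is ordinary practice. Bleeding differs because the protocol has singled it out for special attention. The drug targets tissue factor, which Section 6.1 describes as the main initiator of the extrinsic coagulation pathway, and Section 8.5.1 admits GEN701 patients on stable therapeutic anticoagulation.

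SAP Section 6 provides for "Cancer type (Ovary, Cervix, Endometrium, Bladder, Prostate, Head and neck, Esophagus, Lung". In several of these, an investigator could reasonably regard some bleeding as part of the disease. Such a bleed could be withheld under 11.6.3 at one site and recorded under 11.2 at another. Withholding can only lower the bleeding count, and this single-arm trial has no comparator against which a low count would show up.

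**Working it through.** The plan gives no figure on this point. The check is of the text, followed by an illustration on assumed rates.

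**1. Does any provision bring a withheld bleed back?**

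- *The limit inside 11.6.3.* The exclusion needs the sign to be expected in both intensity and frequency. Bleeding judged to have changed unexpectedly is reported. The reference point is what the indication would produce in the investigator's opinion, not the patient's own state at entry.
- *Deaths.* Section 11.2 makes every death an SAE, including death from progression. Fatal bleeding is captured.
- *Seriousness.* The exclusion covers SAEs as well as AEs, so on its literal wording it reaches non-fatal serious bleeding. The 24-hour rules in 11.3.1 and 11.5 apply to events already classed as AEs and name no exception for bleeding or AESIs.
- *Laboratory data.* Section 11.2 requires clinically significant grade 3 and 4 results to be reported as AEs, but this enters the laboratory finding and not necessarily the bleed. Section 10.3.4 keeps other results out of the eCRF.
- *Relatedness.* Section 11.6.5 assesses relationship to the drug from the first report of an AE. An unreported event gets no assessment.
- *SAP listings.* SAP 11.2 flags AESIs among listed AEs, and SAP 11.3 repeats the same listing for subsets. Apart from the separate listing of deaths, neither section has another route in.
- *Base-trial data.* SAP Section 4 carries over medical history, local tumor assessments and exposure, but not adverse events. Medical history might mention earlier bleeding, but base-trial bleeding AEs are not there to show whether a bleed was a change.

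What remains exposed is non-fatal bleeding that the investigator regards as expected for the tumor in both intensity and frequency.

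**2. How sensitive is a listing of about 25 patients to such omissions?**

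Inputs: n = 25 (expected enrolment, Protocol 12.1); p = true share of patients with a bleeding event (assumed); f = share of those patients left out under 11.6.3 (assumed). The documents give neither p nor f. Patients are treated as independent.

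Expected patients listed = 25 × p × (1 − f).
Chance that at least one is listed = 1 − [1 − p(1 − f)]^25.

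For example, p = 10% and f = 50% give 25 × 0.05 = 1.25 patients and 1 − 0.95^25 = 0.72.

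| p (assumed) | f = 0 | f = 50% | f = 75% |
|---|---|---|---|
| 5% | 1.25; 0.72 | 0.62; 0.47 | 0.31; 0.27 |
| 10% | 2.5; 0.93 | 1.25; 0.72 | 0.62; 0.47 |
| 20% | 5.0; 0.996 | 2.5; 0.93 | 1.25; 0.72 |
| 30% | 7.5; >0.99 | 3.75; 0.98 | 1.88; 0.86 |

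Each cell gives expected patients listed, then the chance of at least one. The proportional loss equals f by construction, so the table is not evidence of how much is lost. It shows only that, if bleeding is uncommon, a few withheld cases could decide whether the AESI appears in the listings at all.

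**The case against.** The strongest reply is that the gap is narrow. The test has two parts, and an unexpected change must be reported. Entrants need stable disease or better (partial response or better if they did not complete base treatment), no radiographic progression, no instability requiring urgent intervention, and ECOG 0 or 1. In controlled disease, new bleeding is harder to call expected. The background to Amendment 3 says that no clinically relevant bleeding had been seen in GEN701. The trial is listings-only, so no planned estimate or decision rule is biased. Finally, 11.2 and 11.6.3 can be read as a general duty and a specific recording instruction, with no contradiction.

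Most of this stands, and it narrows the exposure mainly to stable or recurrent non-fatal bleeding. It does not close the gap. If the specific instruction governs, the reading favors omission. The GEN701 remark does not exclude lower-grade bleeding. In a listings-only trial, complete listings are the whole output.

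A reader might infer more than the documents support:

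- *That all tumor-site bleeding is omitted.* The unexpected-change sentence, the death rule and the general duty in 11.2 all work against this.
- *That the undercount can be quantified.* Neither the bleeding rate nor the share withheld is given. The SAP cancer types are listing categories, not enrolled numbers, and the SAP version history says that no prostate patients are enrolled.
- *That drug-caused and tumor-caused bleeding cannot be told apart clinically.* Nothing in the documents says so, and if it were true the relatedness field could not separate them either.
- *That every serious or grade 3 or higher disease symptom should also be carved out.* The argument rests on bleeding being a named AESI and does not extend that far.

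**Conclusion.** The point holds as a moderate gap in the recording rules. Section 11.6.3 lets an investigator withhold a bleed that 11.1.3 marks as of special interest and that 11.1.1 and 11.2 would have recorded. A withheld event is absent from the primary endpoint and the AESI flag, and it never receives a relatedness judgement. Sites can differ while each follows the protocol.

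The size of the loss is unknown. The conclusion assumes that some investigators would regard some non-fatal bleeding as expected for the tumor. That is an inference from the cancer types, since the documents do not call bleeding expected in any indication.

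**What to change.** Add to the study-disease paragraph of Protocol 11.6.3: 'This exception does not apply to AESIs (Section 11.1.3); these are always recorded as AEs, with relationship to IMP assessed under Section 11.6.5.' Add a cross-reference in 11.2 so that the general duty and the study-disease instruction read as one rule, and repeat it in the eCRF Completion Guidelines. SAP 11.2 needs no change, because its flag will then act on the fuller set of events.

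The cost is small but goes beyond the sentence itself. Some bleeding due to the tumor will be recorded, with the investigator's attribution shown in the relatedness field. Serious events and non-serious events of grade 3 or higher will also go through 24-hour reporting and its follow-up under 11.3.1 and 11.5. The change affects what is recorded, not how patients are managed. If the old wording governed any part of the trial, the report should say that the bleeding listing for that period may be incomplete.

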11.6.4 Information about Infusion-Related Reactions

Information on whether AEs are infusion-related or not must be reported in the eCRF.

11.6.5 Relationship to IMP

The investigator must assess whether or not the event is related to the IMP. If the relationship changes over time, the last judgment by the investigator should be reported. Relatedness has to be assessed and reported from the first time the AE is being reported.

11.6.6 Serious Event

The investigator must indicate whether or not the AE is determined to be “serious” based on what is defined in Section 11.1.

11.6.7 Intensity

The investigator should use the NCI-CTCAE version 4.03 to describe the severity of the AE ([NCI-CTCAE v4.03, 2010](#)).

The grade assigned by the investigator should be the most severe that occurred during the AE period.

11.6.8 Outcome

The outcome of the AE must be judged by the investigator by the following terms:

- Fatal
- Not recovered/not resolved
- Recovered/resolved

- Recovered/resolved with sequelae
- Recovering/resolving
- Unknown

11.6.9 Action Taken with IMP

The action taken with the IMP should be recorded as:

- Dose not changed
- Dose reduced
- Dose interrupted
- Drug withdrawn
- Not applicable
- Unknown

11.7 Follow-up on Adverse Events

All AEs should be followed until they are resolved or until 30 days after the last dose of tisotumab vedotin, until the patient withdraws consent or starts subsequent anti-cancer therapy, whichever occurs first. Serious adverse events, related non-serious grade ≥ 2 ocular AEs and non-serious grade ≥ 3 AEs that are ongoing after trial participation should be followed on a regular basis, according to the investigator's clinical judgment, until the event has been resolved or until the investigator assesses it as chronic and all queries have been resolved.

11.8 Safety Surveillance

Reported individual SAEs, non-serious grade ≥ 3 AEs and non-serious grade ≥ 2 ocular AEs will be evaluated by the sponsor upon receipt. Analysis of aggregated safety data across trials will be performed on an ongoing basis. If new safety issues are identified, actions will be taken as appropriate, including update of the Investigator's Brochure. Safety data obtained in this specific trial will be reported in the Development Safety Update Report.

12. STATISTICAL CONSIDERATIONS

12.1 Sample Size Estimation

Since the trial will include all patients willing to continue on treatment after completing other tisotumab vedotin trials (i.e., GEN701 and GEN702), no sample size determination can be made. It is expected that approximately 25 patients will enter the GCT1015-03 trial.

12.2 Statistical Analyses

Given the low expected number of patients and the heterogeneity between patients at entering this trial with regards to dosing regimen, indication and response to treatment in the lead in trial, no formal statistical analyses are planned. Instead, all endpoints will only be listed. All enrolled patients will be included in the listings.

12.2.1 Efficacy Analyses

Anti-tumor activity endpoints will be listed.

12.2.2 Safety Analyses

Safety endpoints will be listed.

12.2.3 Other Analyses

Not applicable.

12.2.4 Interim Analyses

As this trial may be ongoing for a very long time, potentially several interim analyses may become relevant. Given that it is an open-label trial with no formal hypotheses, this will not require any formal methods such as control of the alpha level. It will simply consist of lists of what has been observed so far with tisotumab vedotin during the trial conduct.

13. MONITORING PROCEDURES/QUALITY ASSURANCE

The sponsor has ethical, legal and scientific obligations to conduct this trial in accordance with established research principles and ICH GCP guidelines E6(R2). As such, in order to fulfill these obligations and to monitor trial progress, the sponsor's monitors or representatives will visit the investigative sites during the trial conduct, in addition to maintaining telephone and written communication. On-site visits, telephone calls and regular review of the eCRFs will be conducted in order to assess patient enrolment, compliance with protocol procedures, completeness and accuracy of data entered on the eCRFs, verification of eCRF data against original source documents and occurrence of AEs. The investigator must provide the monitor, sponsor representative and auditors/inspectors with full access to all source and trial documents.

13.1 Data Collection

As part of the responsibilities assumed by participating in the trial, the investigator agrees to maintain adequate and accurate case histories for the patients treated under this protocol. Case histories include eCRFs and supporting data including, but not limited to, signed and dated ICFs, progress notes, hospital charts, nurse's notes, diary cards or other worksheets provided to patients, laboratory reports, ECG readings, etc.

Patient demographics and key/essential disease baseline characteristics thought to affect outcome, i.e., stratification variables and other prognostic factors, may be collected, as available, for all patients who provide written informed consent. For patients who provided informed consent and were not entered into the trial, the reason the patient was not entered, i.e., did not meet one or more inclusion criteria, met one or more exclusion criteria, or other (e.g., lost to follow-up, consent withdrawn), may also be collected.

